 - Infants 2 to 6 months of age : Three doses of MenACWY-CRM, each of 0.5 ml, is to be given with an interval of at least 2 months; the fourth dose schedule be administered during the second year of life with an interval of at least 6 months after the third dose.
 - Infants 7 to 23 months of age : MenACWY-CRM is to be administered as two doses, each as single dose (0.5ml), with the second dose administered in the second year of life and at least three months after the first dose.
 - 2 to 55 years of age : MenACWY-CRM is to be administered as a single dose (0.5ml).
- * The infant from 2 to 23 months of age may enroll at any point, in the vaccination series, including those subjects who may already initiated vaccination series. According to parental consents, these subjects may be followed up for 29 days within the surveillance period after subsequent vaccination(s) at the same study site.

Non-Safety per protocol set

Subjects excluded from safety per protocol set except for subjects who did not receive MenACWY-CRM and follow-up failure.

Based on rules for estimation of each number of safety evaluation cases, the following local regulation and Guideline on Standards for re-examination for new drugs, etc of MFDS, non-safety analysis set are excluded from the safety analysis set:

Guideline on Standards for re-examination for new drugs, etc (Chapter II, no. 3)

Patient Population for Surveillance:

- A) Patients planned to receive a drug under surveillance by investigator's medical judgment shall be subject.
- B) Subject who do not use within approved range shall not be included in the subject in principal.

However, if data of subject whose use is beyond approved range is collected, perform analysis as a separate item.

	CONFIDENTIAL :	Last Update Date
	THIS DOCUMENT AND INFORMATION CONTAINED HEREIN IS PROPRIETARY TO COMPANY AND IS NOT TO BE DISCLOSED WITHOUT THE WRITTEN PERMISSION OF COMPANY.	26-JAN-2016
STATISTICAL ANALYSIS PLAN(V4.0)		

C) Describe actual selection methods of subject in detail.

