4.1 Safety Endpoints

Safety will be assessed after administration of study vaccine in terms of the number and percentage of subjects with:

- Local and systemic solicited adverse events reported from study Day 1 (day of vaccination) through study Day 7 post-vaccination;
- Unsolicited AEs reported from study Day 1 (day of vaccination) through study Day 7 post-vaccination;
- Medically attended AEs reported from study Day 1 to study termination (Day 29/early termination);
- SAEs reported from study Day 1 to study termination (Day 29/early termination).

5. Assessment Criteria

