6.1 Baseline Characteristics

Descriptive statistics (mean, standard deviation, median, minimum and maximum) for baseline characteristics such as age, height and weight at enrollment will be calculated in the Safety set and Safety per Protocol set.

The following baseline characteristics will be reported:

< Subject Baseline Information >

- gender, age, ethnic origin, children group, weight, height, past diagnosis, kidney disorder, liver disorder, pre-Immunization temperature, temperature location, pregnancy

< Study Vaccine Information >

- vaccine site, number of previous Menveo, study vaccination number, concomitant medications

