6.2.1 Adverse Events by Baseline Characteristics

AE[†]s (as described below) will be reported (n %) for the following baseline characteristics in the safety set and safety per protocol set :

- Age group (2-23 months, 2-10, 11-18, 19-34, 35-55)
- Children group (<18, ≥18)
- Gender (male, female)
- Past diagnosis (yes, no)

	CONFIDENTIAL :	Last Update Date
	THIS DOCUMENT AND INFORMATION CONTAINED HEREIN IS PROPRIETARY TO COMPANY AND IS NOT TO BE DISCLOSED WITHOUT THE WRITTEN PERMISSION OF COMPANY.	26-JAN-2016
STATISTICAL ANALYSIS PLAN(V4.0)		

- Temperature location (axillary, oral, rectal, ear)
- Administration site (left deltoid, right deltoid, left thigh, right thigh, other)
- Concomitant medication (yes, no)
- Kidney disorder (yes, no)
- Liver disorder (yes, no)
- Pregnancy (yes, no)
- Number of previous Menveo (0, 1, 2, 3)
- Study vaccination number (1, 2, 3, 4)

The n(%) of AEs[†] and its 95% confidence interval will be calculated using the normal approximation and analyzed using χ^2 - test. If more than 20% of expected frequencies of the cell counts are less than 5, Fisher's exact test will be used instead of the chi-square test.

[†] AE : AE includes solicited and unsolicited AE (DAY 1-7), medically attended AE (DAY 1-29) and SAE (DAY 1-29).

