7.3 Safety Analyses

- Incidence rate and the number of AEs according to the baseline characteristics (frequency and percentage).
- The number of the expected serious, severity, frequency, action taken, outcome, relationship to MenACWY-CRM for Unsolicited AE (DAY 1-7) and MAAE (DAY 8-29) (frequency and percentage).
- The number of AEs for the severity, day, fever to MenACWY-CRM according to individual solicited AE (DAY 1-7) (frequency and percentage)..
- Incidence rate and number according to the preferred terms of SAE/SADR, unexpected AE/ADR, MAAE/ADR, unsolicited AE/ADR and continuous solicited AE/ADR (frequency and percentage)
- For subjects excluded from safety per protocol set[†] incidence rate and number according to the preferred terms of SAE/SADR, unexpected AE/ADR, MAAE/ADR, unsolicited AE/ADR and continuous solicited AE/ADR (frequency and percentage).

Subject excluded from safety per protocol set: Except for subjects who didn't receive study mediation and follow-up failure.

8. Notes

- Each statistical analysis will be carried out with SAS Software version 9.4 or more recent version.
- In the descriptive statistics, mean, SD, minimum, median, and maximum will be calculated for continuous variables, and frequency and percentage for categorical variables.
- Data including sign of inequality such as “≥20”, “>20” will be excluded from analysis.
- All test statistics will be the results of two-sided tests with the statistical significant level of 0.05.
- The followings shall be included only in re-examination report:
 - Analysis by type of concomitant medications
 - Item ② of paragraph 6.2.3
 - Estimation of 95% confidence interval for incidence of AEs by background factors

Appendix 1

1. Demographic and baseline values, medication characteristics, specific characteristics	6
1.1 Safety Set	6
Table 1.1.1 Total subject.....	6
Table 1.1.2 Demographic characteristics.....	6
Table 1.1.3 Past diagnosis	7
Table 1.1.4 Pre-Immunization temperature	7
Table 1.1.5 Temperature Location.....	8
Table 1.1.6 Administration Site	8
Table 1.1.7 Concomitant medication.....	8
Table 1.1.8 Kidney Disorder	8
Table 1.1.9 Liver disorder.....	10
Table 1.1.10 Pregnancy	10
Table 1.1.11 Number of previous MenACWY	10
Table 1.1.12 Study vaccination number	10
1.2 Safety Per Protocol Set	12
Table 1.2.1 Total subject.....	12
Table 1.2.2 Demographic characteristics.....	12
Table 1.2.3 Past diagnosis	13
Table 1.2.4 Pre-Immunization temperature	13

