Male				X ² -test or Exact test
Female				
Total				

Table 2.1.6 Summary of AE by Past diagnosis

Safety Set	No. subjects with AE n (%)	No. AEs n	Total n (%)	p-value
Yes				X ² -test or Exact test
No				
Total				

Table 2.1.7 Summary of AE by Temperature Location

Safety Set	No. subjects with AE n (%)	No. AEs n	Total n (%)	p-value
Axillary				X ² -test or Exact test
Oral				
Rectal				
Ear				
Total				

Table 2.1.8 Summary of AE by Administration Site

Safety Set	No. subjects with AE n (%)	No. AEs n	Total n (%)	p-value
Left Deltoid				X ² -test or Exact test
Right Deltoid				
Left Thigh (Infant only)				
Right Thigh (Infant only)				
Other				
Total				

Table 2.1.9 Summary of AE by Concomitant medication

Safety Set	No. subjects with AE n (%)	No. AEs n	Total n (%)	p-value
Yes				X ² -test or Exact test
No				
Total				

Table 2.1.10 Summary of AE by Kidney Disorder

Safety Set	No. subjects with AE n (%)	No. AEs n	Total n (%)	p-value
Yes				X ² -test or Exact test
No				
Total				

Table 2.1.11 Summary of AE by Liver disorder

Safety Set	No. subjects with AE n (%)	No. AEs n	Total n (%)	p-value
Yes				X ² -test or Exact test
No				
Total				

Table 2.1.12 Summary of AE by Pregnancy

Safety Set	No. subjects with AE n (%)	No. AEs n	Total n (%)	p-value
Yes				X ² -test or Exact test
No				
Total				

Table 2.1.13 Summary of AE by Number of previous MenACWY

Safety Set	No. subjects with AE n (%)	No. AEs n	Total n (%)	p-value
0				X ² -test or Exact test
1				
2				
3				
Total				

Table 2.1.14 Summary of AE by Study vaccination number

Safety Set	No. subjects with AE n (%)	No. AEs n	Total n (%)	p-value
1				

Safety Set	No. subjects with AE n (%)	No. AEs n	Total n (%)	p-value
2				X ² -test or Exact test
3				
4				
Total				

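### The adverse-event comparison by number of previous Menveo doses is confounded by age and, where later infant doses are followed, by unequal numbers of observed doses

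*SAP*

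**What the plan says.** Section 6.2.1 of SAP V4.0, V5.0 and V6.0 includes "Number of previous Menveo (0, 1, 2, 3" in its list of baseline characteristics. Adverse-event percentages are compared across the levels by chi-square, with Fisher's exact test as the substitute: "If more than 20% of expected frequencies of the cell counts are less than 5". Section 8 (Notes) adds: "All test statistics will be the results of two-sided tests with the statistical significant level of 0.05".

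Section 6.1 reports the factor under study vaccine information: "vaccine site, number of previous Menveo, study vaccination number, concomitant medications". It does not say whether the value is fixed at entry or updated at each dose.

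The shell is in Appendix 1 of V4.0: "Table 2.1.13 Summary of AE by Number of previous MenACWY", with Table 2.2.13 as its per-protocol counterpart. It has rows 0 to 3, a count of subjects with an event, a count of events and one p-value. It has no age restriction and no column for doses observed. Section 4.1 sets the endpoints per subject: "in terms of the number and percentage of subjects with".

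On infants, section 3.1 says: "The infant from 2 to 23 months of age may enroll at any point, in the vaccination series". With parental consent, "these subjects may be followed up for 29 days within the surveillance period after subsequent vaccination(s) at the same study site". The same section gives four doses for infants starting at 2-6 months, two for those starting at 7-23 months, and one at 2-55 years. Nothing in 6.2.1 limits the count to one dose or allows for the number of doses followed.

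**The concern.** A reader of Table 2.1.13 will take it as evidence on whether earlier doses change the safety of the next one. Two other things vary across its rows.

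The first is age. A subject aged 2-55 years vaccinated according to the schedule has no earlier dose and falls in row 0. Rows 1-3 are essentially infants in mid-series. Any difference in event risk between infants and older subjects therefore appears as a difference between row 0 and the rest.

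The second is opportunity to have an event. An infant on the four-dose series can be observed after at most 4, 3, 2 or 1 doses if 0, 1, 2 or 3 were given before entry. On the two-dose series the maximum is 2 or 1. If the count runs over all followed doses, more doses mean a higher chance of at least one event, even at constant risk per dose.

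At stake is a p-value below 0.05 in a regulatory safety report that reflects age or follow-up and is read as an effect of previous doses.

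**Working it through.** **Inputs from the documents.** SAP section 2.2 plans 3,960 subjects, giving about 3,000 evaluable at 2-55 years and 600 at 2-23 months. The total reproduces as 3,600 × 1.10 = 3,960. It does not bear on this test, except that it gives the older cohort's share: 3,000/3,600 = 83%. The maximum numbers of observed doses come from the schedules in section 3.1.

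**Assumptions (not in the documents).** Event risk per dose p is constant and independent between doses, and equal in infants and older subjects unless stated. Of the 600 infants, 300 are in row 0 and 100 in each other row, all on the four-dose series unless stated. A share u of infants is followed for every remaining dose and the rest for one dose.

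**Formulas.** P(any event over k doses) = 1 − (1 − p)^k. The chance of p < 0.05 is from a noncentral chi-square with 3 df.

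**Infants alone, four-dose series, p = 0.30, u = 1.**
- 0 previous: 1 − 0.7⁴ = 76.0%
- 1 previous: 1 − 0.7³ = 65.7%
- 2 previous: 1 − 0.7² = 51.0%
- 3 previous: 30.0%

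**The all-age table as planned, p = 0.30.** Row 0 at u = 1 is (3,000 × 0.30 + 300 × 0.760)/3,300 = (900 + 228)/3,300 = 34.2%.

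| u | Row 0 | Row 1 | Row 2 | Row 3 | Chance of p < 0.05 |
|---|---|---|---|---|---|
| 1 | 34.2% | 65.7% | 51.0% | 30.0% | about 1.0 |
| 0.5 | 32.1% | 47.9% | 40.5% | 30.0% | 0.90 |
| 0.25 | 31.0% | 38.9% | 35.2% | 30.0% | 0.325 |
| 0 | 30.0% | 30.0% | 30.0% | 30.0% | 0.05 |

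Over p = 0.1 to 0.5, the chance of p < 0.05 is at least 0.99 at u = 1, 0.55-0.92 at u = 0.5 and 0.17-0.34 at u = 0.25.

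**Two-dose infants.** If half of rows 0 and 1 are on the two-dose series (infants only, p = 0.30, u = 1), row 0 is 0.5 × 76.0% + 0.5 × 51.0% = 63.5% and row 1 is 0.5 × 65.7% + 0.5 × 30.0% = 47.9%. Rows 2 and 3 stay at 51.0% and 30.0%.

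**Age alone.** Give every subject one observed dose, with infants at 30%.
- Older subjects at 20%: row 0 is (600 + 90)/3,300 = 20.9% against 30% in rows 1-3; chance of p < 0.05 about 0.88.
- Older subjects at 40%: row 0 is (1,200 + 90)/3,300 = 39.1% against 30%; chance about 0.74.

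**After the fix.** Infants only, one dose each: all four rows equal p, and the test would reject at its nominal 5%.

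**The case against.** **Later-dose follow-up is optional.** It needs parental consent, the same site and time left in the surveillance period, and the documents give no expected uptake. An exclusion criterion also bars infants already enrolled for a previous vaccination. That passage and the follow-up provision must be reconciled before the number of windows per infant is clear. This stands: at u = 0 the unequal-dose problem vanishes. The age problem does not.

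**The factor may be recorded at each vaccination.** The SAP never says that it is fixed at entry. If previous doses were updated and tabulated per vaccination, each entry would have one window. This is possible, but the table counts subjects. An infant appearing in several rows would break the independence that a chi-square test assumes. The SAP has to state the unit either way.

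**Infants already have by-dose tables.** Tables 3.1.3, 3.1.8, 7.1.1.1 and 8.1.1.1 are by study vaccination number. The SAP lists that separately from the number of previous doses, so they answer a different question.

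**The analysis is descriptive.** Protocol section 7.1 attaches no hypothesis to the primary safety objective, and this is one of twelve background factors. That limits the importance of the point, but it is also a reason not to print this p-value.

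**A stronger reading.** A reader might infer that incidence must fall steadily as previous doses rise. The documents do not support that. The steady fall needs infants alone, all on the four-dose series and all followed to the end, and no such table is planned. In the all-age table row 0 lies below rows 1 and 2, and mixing the two infant schedules also breaks the order.

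**Conclusion.** The comparison in Tables 2.1.13 and 2.2.13 cannot isolate an effect of previous doses. It is confounded by age whenever event risk differs between infants and subjects aged 2-55 years. It is further confounded by the number of observed doses to the extent that later infant doses are followed. The resulting difference can go either way and need not be a trend.

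The structure comes from the documents: subject-level counting, all ages, no one-dose limit, and about 3,000 single-dose subjects in row 0. The size does not. Event risk, row split, schedule mix and follow-up share are all assumed, and the chance of a spurious p < 0.05 runs from 0.05 to about 1.0 over the follow-up range when risk per dose is equal at all ages. The point merits correction before the table is produced, but it concerns a supporting table and leaves the main safety endpoints untouched.

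**What to change.** In section 6.2.1, for this factor only:
- restrict the analysis to subjects aged 2-23 months;
- define the factor as doses received before the first study vaccination;
- count only events in the 29 days after that vaccination, keeping the existing Day 1-7 and Day 1-29 windows by event type;
- drop the all-age p-value.

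The cost is a short addition to the SAP text and a filter in Tables 2.1.13 and 2.2.13. Later-dose windows are not used here; they remain in the tables by study vaccination number.

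One limit remains. Rows 0 and 1 would still mix the two-dose and four-dose schedules, which start at different ages. Show those rows by schedule, or present them descriptively and say so.

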6.2.2. Analysis of Solicited AE

Frequencies and % of subjects experiencing each adverse event will be presented for each symptom severity. Summary tables showing the occurrence of any local or systemic reaction overall and at each time point will also be presented (see Appendix 1 Table 4.1.3 and 4.2.3).

Post-vaccination adverse events reported from Day 1 to Day 7 will be summarized by maximal severity. The severity of local adverse events for subjects < 6 years of age will be categorized as follows. Injection-site erythema and induration: absent (0 to 9 mm), mild (10 to 25 mm), moderate (26 to 50 mm), severe (> 50 mm); injection-site tenderness: none, mild (minor light reaction to touch), moderate (cried or protested to touch), severe (cried when injected limb was moved). For subjects \geq 6 years, injection-site erythema and induration absent (1 to 24 mm), mild (25 to 50 mm), moderate (51 to 100 mm), severe (>100 mm); pain: none, mild (present but does not interfere with activity), moderate (interferes with activity), severe (prevents daily activity).

For subjects \geq 6 years of age, the severity of systemic adverse events (i.e., chills, nausea, malaise, generalized myalgia, generalized arthralgia, headache) occurring up to 7 days after each vaccination will be categorized as none, mild (present but not interfering with daily activity), moderate (some interference with daily activity), and severe (prevents daily activity) except for rash, which will be

	CONFIDENTIAL :	Last Update Date
	THIS DOCUMENT AND INFORMATION CONTAINED HEREIN IS PROPRIETARY TO COMPANY AND IS NOT TO BE DISCLOSED WITHOUT THE WRITTEN PERMISSION OF COMPANY.	26-JAN-2016
STATISTICAL ANALYSIS PLAN(V4.0)		

categorized as none, urticarial, or other.

For subjects < 6 years of age, the severity of systemic adverse events occurring up to 7 days after each vaccination will be categorized as follows. Change in eating habits : none (no change in appetite), mild (eating less than normal for 1 to feeds), moderate (missed 1 or 2 feeds), severe (missed more than 2 feeds); sleepiness : none (no change in alertness), mild (shows an increased alertness), moderate (sleeps through feeds), severe (sleeps most of the time and it is hard to arouse him/her); irritability : none (no change in child disposition), mild (requires more cudding and he/she is less playful than usual), moderate (more difficult to settle), severe (unable to console); rash : none, urticarial, or other; vomiting : none, mild (1-2 episodes/24 hours), moderate (>2 episodes/24 hours), severe (requires outpatient hydration); diarrhea : none (fewer than 2 loose stools/24 hours), mild (2-3 loose stools or < 400 gms/24 hours), moderate (4-5 stools or 400-800 gms/24 hours), severe (6 or more watery stools or > 800 gms/24 hours or requires outpatient IV hydration).

Body temperature will be categorized as <38°C (no fever), ≥38°C (fever) and will be summarized by 0.5°C increments from 36.0°C up to ≥40°C. Additionally, no fever vs. fever will be reported.

Each local and systemic adverse event will also be categorized as none vs. any.

6.2.3 Analysis of Unsolicited AE

All unsolicited AEs and MAAE recorded in the CRF will be mapped to preferred terms using the most recent MedDRA dictionary and classified by System organ class (SOC) and Preferred Terms (PT). Under the classification standard of MedDRA terms, and all AEs excluding the AEs whose causal relation with the study medication is ‘Not Related’ shall be treated as AEs whose causal relation cannot be excluded {hereafter “Adverse Drug Reaction(ADR)”}.

- ① The frequency and percentage of unsolicited AE (Day 1-7) and MAAE (Day 8-29) according to the expected, serious, severity, frequency, action taken, outcome, relationship to MenACWY-CRM regarding occurred AE will be calculated.
- ② The frequency of unsolicited AEs (Day 1-7) and MAAE (Day 8-29) will be classified into the preferred terms according to the expected, serious, severity, frequency, action taken, outcome, relationship to MenACWY-CRM.
- ③ The number of subjects and percentage of SAE/Serious ADR (SADR), unexpected AE/ADR,

	CONFIDENTIAL :	Last Update Date
	THIS DOCUMENT AND INFORMATION CONTAINED HEREIN IS PROPRIETARY TO COMPANY AND IS NOT TO BE DISCLOSED WITHOUT THE WRITTEN PERMISSION OF COMPANY.	26-JAN-2016
STATISTICAL ANALYSIS PLAN(V4.0)		

MAAE/ADR, unsolicited AE/ADR and continuous solicited AE/ADR will be calculated according to the preferred terms. And the number of subjects and percentage by study vaccination number of SAE/Serious ADR (SADR), unexpected AE/ADR, MAAE/ADR, unsolicited AE/ADR and continuous solicited AE/ADR will be calculated according to the preferred terms in infants 2 to 23 months.

- ④ For subjects excluded from safety per protocol set[†], the number of subjects and the percentage of SAE/Serious ADR (SADR), unexpected AE/ADR, MAAE/ADR, unsolicited AE/ADR and continuous solicited AE/ADR will be calculated according to the preferred terms. And the number of subjects and percentage by study vaccination number of SAE/Serious ADR (SADR), unexpected AE/ADR, MAAE/ADR, unsolicited AE/ADR and continuous solicited AE/ADR will be calculated according to the preferred terms in infants 2 to 23 months.

Subject excluded from safety per protocol set: Except for subjects who didn't receive study vaccination and follow-up failure.

7. List of Table and Data Listings

7.1 Distribution of Subjects

- Number of subjects contracted to the study: The number of subjects are to be collected (under contract) as contracted by the investigator.
- Number of retrieving completed CRFs: Total number of subjects whose completed CRFs.
- Number of safety assessment population: Number of safety assessment population among total number.

7.2 Baseline Characteristics

- Mean and standard deviation (SD) or frequency and percentage by gender, age, ethnic origin, weight, height, past diagnosis, pre-Immunization temperature, temperature location, pregnancy
- Frequency and percentage by vaccine site, number of previous Menveo, study vaccination number, concomitant medications.

	CONFIDENTIAL :	Last Update Date
	THIS DOCUMENT AND INFORMATION CONTAINED HEREIN IS PROPRIETARY TO COMPANY AND IS NOT TO BE DISCLOSED WITHOUT THE WRITTEN PERMISSION OF COMPANY.	26-JAN-2016
STATISTICAL ANALYSIS PLAN(V4.0)		

7.3 Safety Analyses

- Incidence rate and the number of AEs according to the baseline characteristics (frequency and percentage).
- The number of the expected serious, severity, frequency, action taken, outcome, relationship to MenACWY-CRM for Unsolicited AE (DAY 1-7) and MAAE (DAY 8-29) (frequency and percentage).
- The number of AEs for the severity, day, fever to MenACWY-CRM according to individual solicited AE (DAY 1-7) (frequency and percentage)..
- Incidence rate and number according to the preferred terms of SAE/SADR, unexpected AE/ADR, MAAE/ADR, unsolicited AE/ADR and continuous solicited AE/ADR (frequency and percentage)
- For subjects excluded from safety per protocol set[†] incidence rate and number according to the preferred terms of SAE/SADR, unexpected AE/ADR, MAAE/ADR, unsolicited AE/ADR and continuous solicited AE/ADR (frequency and percentage).

Subject excluded from safety per protocol set: Except for subjects who didn't receive study mediation and follow-up failure.

8. Notes

- Each statistical analysis will be carried out with SAS Software version 9.4 or more recent version.
- In the descriptive statistics, mean, SD, minimum, median, and maximum will be calculated for continuous variables, and frequency and percentage for categorical variables.
- Data including sign of inequality such as “≥20”, “>20” will be excluded from analysis.
- All test statistics will be the results of two-sided tests with the statistical significant level of 0.05.
- The followings shall be included only in re-examination report:
 - Analysis by type of concomitant medications
 - Item ② of paragraph 6.2.3
 - Estimation of 95% confidence interval for incidence of AEs by background factors

Appendix 1

1. Demographic and baseline values, medication characteristics, specific characteristics	6
1.1 Safety Set	6
Table 1.1.1 Total subject.....	6
Table 1.1.2 Demographic characteristics.....	6
Table 1.1.3 Past diagnosis	7
Table 1.1.4 Pre-Immunization temperature	7
Table 1.1.5 Temperature Location.....	8
Table 1.1.6 Administration Site	8
Table 1.1.7 Concomitant medication.....	8
Table 1.1.8 Kidney Disorder	8
Table 1.1.9 Liver disorder.....	10
Table 1.1.10 Pregnancy	10
Table 1.1.11 Number of previous MenACWY	10
Table 1.1.12 Study vaccination number	10
1.2 Safety Per Protocol Set	12
Table 1.2.1 Total subject.....	12
Table 1.2.2 Demographic characteristics.....	12
Table 1.2.3 Past diagnosis	13
Table 1.2.4 Pre-Immunization temperature	13
